We propose a pilot and feasibility trial to use continuous glucose monitoring (CGM) in youth with type 2 diabetes (T2D) and public insurance. This feasibility trial would fill a gap in the literature with respect to CGM use in youth with type 2 diabetes. The findings from this trial can provide much needed data to pave the way for future studies using CGM technology in this population. Our proposal is focused on youth with public insurance, seeking to provide diabetes technology for patients and their families to use in daily diabetes management. This pilot is an expansion of our existing program of CGM access to youth with type 1 diabetes which has led to an improvement HbA1C of 0.5% over 1 year and positive feedback from patients and families.^{1,2}

Specific Aim 1: Evaluate the feasibility of CGM start and continuation in youth with T2D and describe glucose metrics and patient reported outcomes (PROs). We will pilot and refine a program to test the hypothesis that CGM start and continuation in youth with T2D is feasible and then evaluate glucose metrics and PROs.

Hypothesis 1a: In phase 1, CGM use exceeding >50% of participants will be feasible and sustainable in youth with T2D, measured by days of CGM use per 2-week period (>75%). **H1b:** Following an additional needs assessment after phase 1, in phase 2 sustained CGM use per 2-week period (>75%) will exceed 75% of participants. **H1c:** Based on completion of PROs surveys, it is expected that diabetes-specific distress will decline, and overall well-being/quality of life will improve. Secondary outcome PROs (see protocol synopsis) collected at baseline will be associated with HbA1c and diabetes management outcomes. Data on glucose metrics, SDOH, and needs and barriers will be described.

Specific Aim 2: To assess the clinical outcomes (HbA1C, time in range [70-180 mg/dL], time in hypoglycemia [<70 mg/dL]) of individuals participating in this trial compared to clinic historical controls.

Hypothesis 2: Use of CGM will improve HbA1C and other clinical metrics of diabetes glucose control.

Measured Outcomes:

1. Sustained use of CGM by patients over one year measured by days of CGM use per every 2-week period with >80% as goal.
2. Change in HbA1C over first year of CGM use
3. Glucose profile metrics: percentage time in range, time in hypoglycemia, and time in hyperglycemia obtained from CGM.
4. Change in weight and BMI over first year of CGM use using clinic visit weight and BMI measurements.
5. PROs

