2. HbA1C greater than 6.5% at enrollment. This is to enroll patients who are working on improving glucose control but are still not meeting HbA1c targets.^{9,25}
3. Interested in starting on a continuous glucose monitor
4. Access to a mobile device that is compatible with CGM applications or willing to use CGM receiver which will be provided. Both the receiver and mobile device allows patients to view glucose data and alerts from the CGM and upload glucose data during or in between in-person or virtual clinic visits, not necessitating that the participant have access to a mobile device.
5. Public insurance
6. Age 4-20 years inclusive

Exclusion criteria

1. Non-T2D diagnosis
2. HgA1C < 6.5%
3. Participant not willing to wear CGM
4. Private insurance

Procedures and Methods

Recruitment: The study team will review clinic schedules to identify youth with T2D from the patients in our clinic who would qualify. The informed consent process will be conducted prior to initiating the study. Following CGM initiation by a CDE, youth will have a routine 1-week clinic follow up with our diabetes team and then will be seen per clinic standard of care, every 3 months thereafter for the 12 months of the study duration. At each visit we will collect descriptive data on CGM use, CGM glucose metrics, and provide CGM supplies. PROs will be evaluated at three time points during the study. In phase 2, we will identify a new cohort of eligible patients who will be evaluated at a similar cadence as phase 1.

Visit	1	2	2a	3	3a	4	4a	5	5a	6
Weeks from start	x	2 weeks	4-6 weeks	12 weeks						
Informed consent and assent Visit Type ** this will be modified if LibreView App is available during study duration, can move visits to TH with lab A1C	x (can be done in person or via TH)									
	In person	IP/TH	phone/IP	IP	phone/IP	IP	phone/IP	IP	phone/IP	IP
Demographics	x									
Diabetes History	x									
HbA1C	x			x		x		x		x
CGM start	x				x					x
PROs	x			x						x
CGM metrics	x	x	x	x		x		x		x
CGM education	x	x	x			x		x		x
CRC check on supplies (confirm use and shipment)	x	x	x	x	x	x	x	x	x	x
Final study visit										x

Visit 1:

- Participants will be offered the opportunity to start on CGM at their scheduled clinic visit
- Participants will receive CGM education from a certified diabetes educator (CDE)

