- The care team member initiating the CGM will ask patients and their caregivers if they are interested in hearing about this study to understand the use of CGM in youth with type 2 diabetes
- If a patient and/or caregiver is interested in this study, one of the study team members will discuss the study with the participant and obtain informed consent and assent (if needed).
- Participants who consent to be part of this study will have the appropriate CGM applications and readers active (Libre 2 CGM, LibreView, LibreLink) as per standard clinical care.

1. Informed consent and assent - this can be done in person or virtually
2. CGM start – done by CDE in clinic
 - a. 4 weeks of supplies given – CRC to confirm with family preferred way to get supplies every 6 weeks and best way to contact them.
 - b. Standard clinic CGM education
3. Routine clinic visit

4. PRO completion - participants who speak and write English and Spanish will be asked to complete PROs surveys

Visits 2a,3a,4a,5a:

1. CRC check in with family/patient
 - a. Confirm CGM use
 - b. Address CGM issues – CRC to address or forward to CDE if clinical question
 - c. Ship or arrange for supply pick up (6 weeks of supplies)
 - d. Confirm next clinic visit

Visits 2,3,4,5,6:

[figure not shown]
1. Routine Clinic visit including CDE visit. The purpose of these visits is to reinforce prior teaching, answer questions, and review CGM data, making changes as necessary to the patient's care regimen to better control their diabetes.
2. CRC check in, supplies provided (for all visits except visit 6)
3. PRO questionnaires administered for visits 3 and 6

Biostatistical plan

Statistical methods: We will generate descriptive statistics for all participants included in the study and will create a STROBE diagram²⁶ to describe participants screened, recruited, and followed in both study phases. To address the feasibility of CGM use in T2D, we will estimate the proportion of participants who have sustained CGM use in both phase 1 and 2. Our feasibility analysis will include all participants. To address H1c, we will fit linear regression models using GEE to estimate the association of PROs with longitudinal HbA1c. Logistic regression models fit with GEE will be used to estimate the association of PROs with dichotomous diabetes management outcomes (e.g., presence of diabetes distress).

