At each visit we will collect descriptive data on CGM use, clinical glucose outcome metrics, and provide CGM supplies. Mixed affects modeling will be used to characterize the trajectory of measured variables and to account for patient-level correlation of this data. To account for gaps in CGM use we will use intention to treat analysis and consider a censoring method for a patient who leaves the practice or are lost to follow up. We will also perform an exploratory analysis of the relationship at a patient-level between days of CGM wear and time in range.

Study Timeline

Data Collection and Entry

1. Study participant data entry will be collected and entered in Stanford RedCap by the study team.
2. PRO will be collected in RedCap

The initial survey is filled out in person during the CGM visit during which, parents provide an email that will be the platform for contact for the future surveys. At the follow up points, the RedCap data base will automatically trigger survey link to the email on file. If the survey is not completed, a second email is sent as a reminder followed by provider team reminders. Participant data will be included for analysis for the time frames that are available when.

These measures will assess issues of adherence or illness distress and provide valuable information for providers to better understand the impact of early CGM initiation. The patient/guardian will have the option of filling out the questionnaires in English or Spanish. Based on the evidence in the PROs literature and our clinical experiences, we have developed an algorithm for responding to PROs screen scores that are outside of the normative range triggers a response from social worker and/or diabetes psychologist²⁷. Study personnel will complete a chart review to collect relevant health information including diagnosis, duration of disease, indicators of health status, and regimen information (e.g. medication, doses). These medical record data are required to assess the validity and usefulness of the clinical PROs screening measures. Additionally, reliability analysis will be conducted to examine the psychometric properties of the PROs measures, and the satisfaction questionnaire data will be aggregated to assess the acceptability of the PROs procedure from the patient's perspective.

- PROMIS global health (youth): BELOW 22 for the PROMIS global health scale. Anyone who scores 21 or lower would trigger an alert to place a diabetes psychology referral.

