Problem Areas in Diabetes – Pediatric (Diabetes Burden)	Youth 8-17 and all parents	YOUTH – Youth will complete this survey on psychological distress and burden associated with taking care of diabetes. Child survey for 8-11 years, Teen survey for 12-17 years. PARENTS – complete a proxy version as well as a report of their own distress.
Use of and Comfort with Technology	Youth ≥ 11 , All parents	YOUTH – Youth ages 11-18 will complete this survey on use of and comfort with general technology and diabetes devices. PARENT – All parents complete the same questions on technology and devices.
PROMIS Global Health scale (PGH-7)	Youth ≥ 11	YOUTH – Youth will complete this survey on their overall health, integrating patient experiences across physical, mental and social health

Community Partnership and Engagement

Once complete, results from this study will be shared with medical leadership of California Children's Services (public insurance which provides coverage of diabetes-related care for our youth with type 2 diabetes) at the state and county level to advocate for coverage and access to CGM technology for all youth with type 2 diabetes. We will also engage with the Pediatric Endocrinology Family Advisory Counsel at Stanford Children's Health to combine results from this study with patient/parent advocacy efforts to gain insurance coverage for CGM in all youth with T2D.

Potential Pitfalls and Contingency Plans

Study participants are asked to attend clinic appointments as recommended by their care provider. Our clinic standard is to have patients attend at least 4 visit per year, on average 1 clinic visit every 3 months. There may be missed appointments. Efforts will be made to remind families of appointments the day before the visit by phone or MyChart messaging. If a patient misses an appointment, the team will make efforts to re-schedule the appointment and address barriers to attending clinic appointments.

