Participants may have challenges with CGM supplies, upload of glucose data, or questions about CGM use. Our team will be available to patients and their families to address these issues including attempts to avoid gaps in CGM supplies to support continuous use of CGM. If a patient misses more than 3 appointments or decides to stop using CGM they will be withdrawn from the study and asked to resume usual care. We are in the process of obtaining CGM supplies for all participants for the duration of the study to ensure continued access to CGM supplies. If we are not able to secure funding for CGM supplies we will use budgeted funds from this grant to cover the cost of CGM supplies for 50 participants over 6 months in place of salary support for a research assistant and home HbA1C kits, with the PI salary support going towards PI FTE towards completing study related tasks and working with participants to facilitate an in-person clinic visit. Even with a shorter duration, the study can provide meaningful pilot data about the feasibility of CGM use and key clinical outcomes in youth with T2D.

Future Steps

Data from this feasibility trial would fill a gap in the literature with respect to CGM use in youth with type 2 diabetes. The findings from this trial can provide much needed data to impact CGM coverage policy for publicly insured youth with type 2 diabetes in California and pave the way for future studies using CGM technology in this population.

References

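### Participants who stop CGM for good are withdrawn with no later outcome collection, which conflicts with the intention-to-treat analysis planned for gaps in CGM use

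*Combined protocol and SAP*

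**What the plan says.** **Withdrawal.** Potential Pitfalls and Contingency Plans covers two groups: those who miss more than three appointments and those who stop CGM. For the second group the rule is that a patient who "decides to stop using CGM they will be withdrawn from the study and asked to resume usual care".

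**Analysis.** The Biostatistical plan states: "To account for gaps in CGM use we will use intention to treat analysis". It adds that censoring will be considered for patients who leave the practice or are lost to follow-up. It plans mixed models for the trajectories of measured variables, and a feasibility analysis that includes everyone.

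**PROs.** Procedures and Methods says "PROs will be evaluated at three time points during the study". The schedule table marks visits 1, 3 and 6, and the visit list confirms "PRO questionnaires administered for visits 3 and 6" after the baseline set. Hypothesis 1c is directional: "it is expected that diabetes-specific distress will decline, and overall well-being/quality of life will improve".

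**Routes by which later data could arrive.** Data Collection and Entry says "At the follow up points, the RedCap data base will automatically trigger survey link to the email on file", and also "Study personnel will complete a chart review to collect relevant health information". On usual care, the contingency section says "Our clinic standard is to have patients attend at least 4 visit per year, on average 1 clinic visit every 3 months". None of these sentences mentions withdrawn participants.

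**The concern.** Intention to treat needs outcomes from participants whether or not they keep using the device. The withdrawal rule ends study participation because the device is no longer used. If both are followed as written, the participants for whom the analysis principle matters most have no provision for later data.

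The outcomes at stake are the one-year changes in HbA1c, weight/BMI and PROs (Measured Outcomes 2, 4 and 5), and the HbA1c part of the Aim 2 comparison with historical controls. Each could come to describe mainly the participants who kept wearing CGM. The protocol means to take the results to public-insurance leadership to argue for coverage, so which participants the figures describe is important.

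**Working it through.** The plan gives no stopping rate, standard deviation or sample-size calculation, so there is no figure of its own to reproduce. The check is first textual, then illustrative.

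**Step 1. Does any other text repair the conflict?**
- The censoring clause names leaving the practice and loss to follow-up. A participant who stops CGM and returns to usual care has done neither.
- The chart review has a stated purpose, which is to assess the PRO screening measures. It does not mention outcome follow-up or the period after withdrawal.
- The available-data sentence in Data Collection and Entry is unfinished. It concerns the use of data already obtained, not further collection.
- The schedule table and visit lists describe people who are in the study.

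Nothing repairs it.

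**Step 2. PRO sets per stopper.** Sets are due at visits 1, 3 and 6. Withdrawal before visit 3 leaves one of three. Withdrawal between visits 3 and 6 leaves at most two of three. Neither has a 12-month set. The number without a 12-month set is (assumed stopping rate) × n, with n = 30 and 50 from the Design section:

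| Assumed stopping | Phase 1 (n = 30) | Phase 2 (n = 50) |
|---|---|---|
| 10% | 3 | 5 |
| 20% | 6 | 10 |
| 40% | 12 | 20 |

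This is before ordinary non-response.

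**Step 3. HbA1c, if chart values are not extracted after withdrawal.** In a simple comparison of means, the retained-only mean minus the all-participant mean is w × (d_continue − d_stop), where w is the share withdrawn. With w = 0.20, d_continue = −0.5 and d_stop = 0, this is 0.20 × (−0.5) = −0.10, so the reduction is overstated by 0.10 points. The sign reverses if stoppers do better than continuers.

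The plan uses mixed models, which keep values up to withdrawal, so I also computed the expected estimate from a random-intercept model. Assumptions:
- five equally spaced HbA1c visits (1, 3, 4, 5 and 6)
- between-person SD 1.5 and within-person SD 0.8
- a stopper's last observed visit equally likely to be 1, 3, 4 or 5
- on-CGM change −0.5. This is the type 1 programme figure in Specific Aims, so it does not come from this population.

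Each row compares the same model with full follow-up and with withdrawal, at 20% stopping:

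| Model | Onset of effect | Stoppers | Full follow-up | With withdrawal | Shift |
|---|---|---|---|---|---|
| Visit means | by week 12 | return to baseline | −0.400 | −0.500 | 0.10 |
| Visit means | by week 12 | never respond | −0.400 | −0.453 | 0.05 |
| Visit means | linear | return to baseline | −0.400 | −0.500 | 0.10 |
| Visit means | linear | never respond | −0.400 | −0.481 | 0.08 |
| Linear trend | by week 12 | return to baseline | −0.300 | −0.419 | 0.12 |
| Linear trend | by week 12 | never respond | −0.320 | −0.388 | 0.07 |
| Linear trend | linear | return to baseline | −0.400 | −0.500 | 0.10 |
| Linear trend | linear | never respond | −0.400 | −0.479 | 0.08 |

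If stoppers keep the benefit, the shift is 0 in three of the four model and onset combinations. In the fourth (linear trend, onset by week 12) it is 0.02. The range when benefit is absent or lost is 0.03 to 0.06 at 10% stopping and 0.10 to 0.25 at 40%. With −0.4 (the adult type 2 trial cited in Background) all shifts are multiplied by 0.8, so 0.05 to 0.12 becomes about 0.04 to 0.10.

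**Step 4. Scale.** With the same within-person SD, the standard error of a mean change is 0.8 × √(2/30) = 0.21 in phase 1 and 0.8 × √(2/50) = 0.16 in phase 2. At 10% or 20% stopping, the shift is below either.

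**The case against.** Several points on the other side are sound.

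- **Scope.** A temporary gap does not trigger withdrawal, so intention to treat remains workable for gaps in the ordinary sense. Many participants withdrawn for missed appointments would fall under the loss-to-follow-up clause. Both points stand, and they confine the conflict to people who decide to stop.
- **Target.** Measured Outcomes 2 and 4 refer to change over the first year of CGM use. That can be read as an on-use quantity, for which ending follow-up at stopping is coherent. The intention-to-treat sentence points the other way. The plan has to say which it means.
- **Availability.** Stoppers return to usual care, probably in the same clinic, so HbA1c and weight are likely to be in the chart. If they are extracted, the HbA1c shift is 0. This stands, but the plan does not say that they will be.
- **Model.** The mixed model uses values obtained before withdrawal. It does so validly only if later values are missing at random given the earlier ones, which the plan does not state and which stopping the device may breach.
- **Hypothesis 1c.** The model named for it relates PROs to HbA1c and does not estimate 12-month PRO change. Even so, the hypothesis predicts change, and PROs are a measured outcome.

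A reader might infer more than the documents support. One inference is that results must be biased in favour of CGM. The direction rests on how stoppers fare, which the documents do not say. Another is that the sustained-use proportion is inflated because stoppers drop out of it. The Biostatistical plan keeps all participants in that analysis and the outcome runs over one year, so the natural reading already counts a stopper as not sustained.

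**Conclusion.** The conflict is real for participants who stop CGM permanently, and it is in the text rather than inferred. The loss of 12-month PROs follows directly from the rule and the schedule. The loss of HbA1c and weight/BMI is conditional on chart values not being extracted after withdrawal. Within Aim 2 only HbA1c is affected, because CGM glucose metrics cannot exist once the device is off.

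The size cannot be established. The illustrative HbA1c shift of 0.05 to 0.12 points at 20% stopping rests on an assumed stopping rate, effect, SDs and stopper outcomes. It would be hard to see against sampling error in either phase. It would not shrink with more participants, however, and could carry into the studies that this pilot is meant to inform. PROs not collected at the time cannot be recovered later, so the point should be settled before anyone is withdrawn. It is a should-fix.

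**What to change.** Reconcile the contingency section with the Biostatistical plan by separating stopping CGM from leaving the study. This concerns data collection only; it proposes no change to device use or care.

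1. Unless consent is withdrawn, continue to extract routine clinic HbA1c, weight and BMI from the chart after a participant stops CGM.
2. Continue to send the automated PRO surveys due at visits 3 and 6.
3. Include these values in the intention-to-treat analysis.
4. State that one-year change means the year after CGM start. Add an on-use analysis as supplementary if it is wanted.
5. Show the number and timing of stoppers in the planned STROBE diagram.

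The cost is a change of protocol wording, a few more chart extractions, and survey e-mails that are already automated. The consent terms are not in the copy reviewed, so whether they allow later data use has to be checked. The existing response to out-of-range PRO scores would also apply to these surveys and needs staff cover. The reported figures may turn out less favourable.
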